10 SAFETY REPORTING

Safety reporting for each participant will begin from the time of consent and will end when the participant has reached their final follow up time point, at 5 years post-diagnosis. Investigators should follow up serious adverse events until resolved or the participant reaches 5 years post-diagnosis.

All unexpected serious adverse events (SAEs) are to be reported according to the guidelines specified in section 15 of the Master Protocol.

10.1 Related and expected Serious Adverse Events

These will be as per the master protocol.

11 STATISTICS & ANALYSES

11.1 Sample size determination

The sample size for this study will be 878 participants.

Clinical Research Protocol Template version 15.0 CONFIDENTIAL © Copyright: The University of Oxford and Oxford University Hospitals NHS Foundation Trust 2019 Page 21 of 27 Evidence on EQ-5D-3L utility values in similar patients is available from trials performed within the WHITE cohort and WHITE trials.^{17 18} These data suggest that the standard deviation for EQ5D-3L at 4 months postdiagnosis is approximately 0.3. The best evidence we have for an appropriate minimum clinically important difference (MCID) is for EQ-5D-3; published estimates for MCID are in the range 0.05 to 0.085,¹⁹ so an upper limit for the standardised effect size in hip fracture of approximately 2.8 or a 'small to moderate effect' based on Cohen's criteria.²⁰

Assuming that the EQ-5D-5L at 4 months post-diagnosis has an approximate normal distribution, which is reasonable,^{17 18 21} and a 1:1 allocation ratio, then if the true difference between the mean EQ-5D-5L in the two groups is 0.085, and the standard deviation is 0.3, we will need to recruit 263 participants in each group to be able to reject the null hypothesis that the population means are equal with 90% power and 5% (2-sided) significance. In a similar population from the WHiTE 3¹⁸ and WHiTE 4²² trials loss to follow-up was considerable, with 10% due to death prior to the four months timepoint, 20% for other types of loss to follow-up and 20% post-randomisation withdrawals (due to participants declining consent on the recovery of capacity – see paragraph 9.2). As deaths can be incorporated into the utility scores, with a score of 0, we would assume that 60% of recruited study participants will provide the primary outcome. In summary, a minimum of 526 participants with primary outcome data are required to allow us to detect a difference of 0.085 assuming a standard deviation of 0.3 with 90% power and a 5% 2-sided significance. To ensure this while allowing for 40% loss to follow-up gives an anticipated target of 878 randomised participants (439 per arm).^{18 22}

11.2 Analysis populations

The primary analysis population will be intention to treat (ITT); that is all participants will be analysed as randomised. Sensitivity analyses will be undertaken on the per-protocol population for the primary outcome and key secondary outcomes.

The ITT population includes all randomised participants including:

- 1. Participants who are randomised but do not undergo surgery (such as those who died or were found to be ineligible after randomisation but before surgery).
- 2. Participants who are randomised and die after surgery with a consultee declaration signed but before post-diagnosis consent has been confirmed.
- 3. Participants who are randomised and found to be ineligible during or after surgery.

Note: participants who withdraw from the comparison between randomisation and 5 years will provide data up to the point of withdrawal.

The per protocol population will be the ITT population excluding participants as described in 1 and 3 above and other major deviations from the protocol which will be fully described in the Statistical Analysis Plan.

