9.1.2 Inclusion criteria

• A minimally displaced intracapsular hip fracture, that in the opinion of the treating surgeon may benefit from surgical treatment.

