9.1.3 Exclusion criteria

The participant is not eligible if ANY of the following apply:

- The fracture is only apparent on cross-sectional imaging.
- In the opinion of the treating surgeon the fracture cannot be fixed without a reduction manoeuvre.
- The fracture is complicated by local tumour deposits.
- There is clinically relevant pre-existing osteoarthrosis (OA) of the ipsilateral hip joint.

The incidence of severe OA in patients sustaining minimally displaced fractures is extremely rare (less than 5%).¹³ Patients will be assessed by the treating surgeon to determine if there is clinically significant preexisting functional pain that limits their mobility.

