9.3 Randomisation

Randomisation will be as per section 11.5 of the platform protocol. Randomisation will be on a 1:1 basis to arthroplasty or internal fixation, stratified by recruitment centre. The allocation sequence will be generated by the trial statistician. Full details will be stored in a separate randomisation and blinding plan stored in the confidential statistics section of the trial master file.

Randomisation will be performed as close to the start of surgery as possible to avoid the risk of postponement of surgery or moving to a different theatre list.

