9.5.3 Surgical treatment

All participants will receive perioperative prophylactic antibiotics in accordance with current protocols agreed at each centre. Appropriate preparation, positioning and anaesthetic technique will be left to the discretion of the clinical team as per their normal clinical practice. Resources related to delivering treatment in both arms will be collected in study case report forms, including type of intervention received, admission and discharge date, complications and further treatments required. Participants will be randomly allocated to one of the treatment arms:

INTERNAL FIXATION

Internal fixation is usually performed using either a sliding hip screw or cannulated screws, with a recent trial showing no difference in outcome.¹⁴ We will take a pragmatic approach, allowing surgeons to follow their usual practice for internal fixation.

Intraoperative fluoroscopy will be used to confirm that the fracture has not significantly displaced. The fracture will be fixed in-situ with no attempt to manipulate the fracture by closed or open means. Fixation will be achieved using a technique and implant chosen by the operating surgeon.

HIP REPLACEMENT

One of two types of hip replacement may be offered to people with hip fractures - hemiarthroplasty and total hip arthroplasty (THR). Patient position, surgical approach, implant and surgical technique will be chosen by the operating surgeon.

Details of the operation will be recorded in the study CRF.

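### The per-protocol set excludes participants found ineligible during or after surgery, and the chance of such a finding can differ by arm, so the per-protocol sensitivity analysis can be biased

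*Protocol*

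**What the plan says.** Section 11.2 makes intention to treat the primary population and gives the per-protocol set a defined use: "Sensitivity analyses will be undertaken on the per-protocol population for the primary outcome and key secondary outcomes". The set is then defined: "The per protocol population will be the ITT population excluding participants as described in 1 and 3 above". Group 3 reads: "Participants who are randomised and found to be ineligible during or after surgery". Other major deviations are left to the SAP, but the removal of groups 1 and 3 is settled in the protocol.

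Eligibility depends on displacement. Section 9.1.2 requires "A minimally displaced intracapsular hip fracture, that in the opinion of the treating surgeon may benefit from surgical treatment", and section 9.1.3 excludes a participant if "In the opinion of the treating surgeon the fracture cannot be fixed without a reduction manoeuvre". The other exclusions in 9.1.3 are a fracture seen only on cross-sectional imaging, local tumour deposits, and clinically relevant osteoarthrosis of the same hip.

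On timing, section 9.3 says "Randomisation will be performed as close to the start of surgery as possible", so anything found in theatre is found after allocation. Section 9.4 accepts that the treating team cannot be blinded.

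Section 9.5.3 says under internal fixation: "Intraoperative fluoroscopy will be used to confirm that the fracture has not significantly displaced". Under hip replacement it describes no such check and says "Patient position, surgical approach, implant and surgical technique will be chosen by the operating surgeon".

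**The concern.** A per-protocol set keeps the arms comparable only if its exclusions would have fallen on the same kinds of participant in either arm. Group 3 does not secure this. Whether a participant is found ineligible depends on what the surgeon looks at, and that depends on the allocated operation. A fracture that looked minimally displaced beforehand but is displaced in theatre has a stated route to detection under fixation and none under replacement. Conversely, tumour or joint disease might be noticed more readily when the joint is opened and bone is removed. Two of the criteria also rest on the opinion of the treating surgeon, who by then knows the allocation.

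At stake is the reading of the named sensitivity analysis. If it departs from the intention-to-treat result, a reader cannot tell an effect of adherence and eligibility from an effect of unequal detection.

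**Working it through.** **Context from the protocol (section 11.1).** Target difference 0.085, standard deviation 0.3, 90% power, two-sided 5%, 263 per group with outcome data, 439 per arm randomised. The stated size reproduces: the normal approximation gives 262 per group and the noncentral t gives 263 (power 0.9003); 526 / 0.60 = 876.7, so 877, or 878 as an even total. The standard error of the difference at 263 per group is 0.3 × √(2/263) = 0.0262. These figures serve only as a yardstick.

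**The two arms side by side.**

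| | Internal fixation | Hip replacement |
|---|---|---|
| Intraoperative check for displacement | Stated (fluoroscopy) | None stated |
| Fracture still visible after surgery | Yes | No; the fractured part is removed (section 6.1) |
| Joint opened and bone removed | Not described | Yes |
| Surgeon knows the allocation | Yes | Yes |

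**Bias through displacement.** Let q be the share of fractures displaced in theatre and d_R the amount by which those participants score lower on EQ-5D after replacement. Suppose fixation detects and drops all of them and replacement drops a fraction r. The fixation arm then holds only eligible participants, and displaced fractures make up q(1 − r)/(1 − rq) of the replacement arm. Against a comparison of eligible participants,

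bias in favour of fixation = d_R × q(1 − r)/(1 − rq).

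The relevant deficit is the one after replacement. The rise in the fixation mean when displaced fractures are dropped is what a per-protocol exclusion is meant to produce; the bias is what remains in the other arm.

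The protocol gives none of q, d_R or r. Assumed ranges: q = 1% to 10%, d_R = 0 to 0.20.

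| q | d_R | r | Dropped, fixation / replacement (of 439 each) | Bias | Share of 0.085 | In SEs |
|---|---|---|---|---|---|---|
| any | 0 | any | – | 0 | 0% | 0 |
| 1% | 0.05 | 0 | 4.4 / 0 | 0.0005 | 0.6% | 0.02 |
| 5% | 0.10 | 0 | 22.0 / 0 | 0.005 | 5.9% | 0.19 |
| 5% | 0.10 | 0.5 | 22.0 / 11.0 | 0.0026 | 3.0% | 0.10 |
| 10% | 0.20 | 0 | 43.9 / 0 | 0.020 | 23.5% | 0.76 |
| 10% | 0.20 | 0.5 | 43.9 / 22.0 | 0.0105 | 12.4% | 0.40 |
| any | any | 1 | equal | 0 | 0% | 0 |

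With the standard error held at 0.0262, a bias of 0.005 takes the two-sided type I error of the per-protocol comparison from 5% to 5.4%. A bias of 0.020 takes it to 11.9% and cuts power for a true 0.085 benefit of replacement from 90% to 70%.

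**The opposite route.** If a share q′ has tumour or osteoarthrosis found only in the replacement arm, the same formula applies with the arms exchanged, and it favours replacement where such participants do worse after fixation. With q′ = 2% and a deficit of 0.10 (assumed), the shift is about 0.02 × 0.10 = 0.002. Set against displacement at q = 5%, d_R = 0.10, the net is about 0.005 − 0.002 = 0.003 towards fixation. Set against q = 1%, d_R = 0.10, it is about 0.001 − 0.002 = −0.001, that is, towards replacement. The sign depends on quantities the protocol does not give.

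**The case against.** The strongest reply has four parts.

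- **Displacement in theatre is not called ineligibility.** The fluoroscopy sentence can be read as a check for change since diagnosis, and the reduction criterion as a judgement made at enrolment. A fracture that met the criteria at randomisation and then moved might be handled as a treatment deviation, which section 11.2 leaves to the SAP. This stands: the link from fluoroscopy to group 3 is an inference from sections 9.1.2, 9.1.3 and 9.5.3.
- **Silence is not absence.** A surgeon performing a replacement may notice displacement, and sections 8.1.2 and 9.6.2 provide for radiographs from both arms up to 12 months. This reduces the imbalance (the rows with r = 0.5). It does not remove it, because postoperative films cannot show a fracture that has been excised.
- **Direction.** A reader might infer that the per-protocol analysis is tilted towards fixation. The documents do not support that as a flat statement. It would need displaced fractures also to do worse after replacement, and it ignores tumour and osteoarthrosis, which could work the other way. Only a conditional form is defensible: through displacement alone, and if that deficit exists, the bias would probably favour fixation.
- **Consequence.** A reader might also infer that the sensitivity analysis cannot test the robustness of the main result. That goes too far. Under modest assumptions the bias is a small fraction of a standard error, no decision rule hangs on this analysis, and the intention-to-treat analysis retains group 3.

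None of this answers the core point: the protocol itself fixes an exclusion made after randomisation, with allocation known, on findings whose detection can depend on the arm.

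**Conclusion.** The point holds as a defect in how the per-protocol set is defined. Exclusion for ineligibility found during or after surgery can operate differently in the two arms, so the per-protocol sensitivity analysis of the primary and key secondary outcomes can be biased. Neither direction nor size can be determined from the protocol. Through displacement alone the illustrative range is 0 to 0.020 EQ-5D units (up to about 24% of the 0.085 target), resting on an assumed 1% to 10% displaced in theatre, an assumed deficit of 0 to 0.20 after replacement, full detection under fixation, and the inference that such cases would be classed as ineligible. The intention-to-treat primary analysis is untouched. This is a low-cost improvement to a supporting analysis, not a threat to the main conclusion.

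**What to change.** Reword the per-protocol definition in section 11.2, and carry it into the SAP, so that:

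- eligibility-based exclusions are limited to criteria failed on information available before randomisation (the pre-operative radiograph and the eligibility form), assessed the same way in both arms and without reference to allocation;
- no participant is excluded on a finding made only during or after surgery;
- such findings, intraoperative displacement included, are tabulated by arm and reason.

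The same rule should cover the participants in group 1 who are there because they were found ineligible. The material should exist for both arms: section 9.5.1 has the diagnosis confirmed by plain radiograph. With exclusions made alike in both arms (r = 1), the bias term above is zero.

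The cost is protocol and SAP wording, an eligibility assessment made without reference to allocation, and a slightly less pure per-protocol set, since some participants whose ineligibility emerged only in theatre will stay in. No clinical procedure changes.

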11.3 The level of statistical significance

The statistical significance will be assessed at 5% for two-sided tests and reported for p-values less than 5% (p values of less than 0.05). All p-values will be reported to 3 decimal places. 95% confidence intervals will be reported throughout.

11.4 Health economic analysis

A fully detailed economic evaluation analysis plan (HEAP) will be drafted early in the trial and finalised after review by the DSMC and TSC. The economic evaluation will determine cost-effectiveness in relation

Clinical Research Protocol Template version 15.0 CONFIDENTIAL © Copyright: The University of Oxford and Oxford University Hospitals NHS Foundation Trust 2019 Page 22 of 27 to quality-adjusted life years (QALYs) from an NHS and personal social services perspective at 12 months post intervention. Fractures in this elderly population may burden their carers and it is possible that different treatment pathways will have different consequences on their families and friends. As such, we will report separately private expenses, informal care, and productivity losses incurred in both arms.

Any missing QALYs and costs will be jointly imputed using multiple imputation chained equations. Cost and QALY estimates will be bootstrapped and adjusted for trial stratification variables (centre) and other potential variables as per the statistical analysis plan, such as age, gender and cognitive impairment, in secondary analyses. "All available" and "imputed" cost categories and QALY data, will be reported by trial arm in a cost-consequences framework. The cost-effectiveness parameter will be the bootstrapped incremental net monetary benefit statistic (INMB) derived using the UK societal willingness to pay thresholds of £20,000 and £30,000 per QALY. The INMB estimates if society is willing to pay more for the health benefit (QALY gained) than the incremental cost of the intervention. Positive values indicate the intervention is cost-effective. In a cost-effectiveness acceptability curve, we will depict the probability of the interventions being cost-effective at a range of willingness to pay thresholds to illustrate the uncertainty around the adoption decision. In one-way and sensitivity analyses we will vary methodological assumptions to gauge robustness of results.

In a secondary analysis, for comparable results with the planned 5 years economic evaluation, we will reestimate the cost-effectiveness parameter at 12 months using secondary care inpatient and emergency department cost data only.

11.5 Long-term analyses

The first long-term analysis will be reported when each living participant has reached five years of followup.

Hospital data will be received at episode level (period of time a patient is under the care of a consultant), from which spells of continuous care will be built. For each treatment group, statistical models will be estimated to investigate the association between treatment and death and re-operations. Operations for infections and dislocations will be identified by a combination of corresponding International Classification of Diseases (ICD; diagnostic) and Office of Population Censuses and Surveys (OPCS; procedure) codes, whilst all-cause reoperations will be identified by OPCS codes only. Similar work has been undertaken before by [name] as well as other researchers, with relevant codes readily available.²³⁻²⁵ Reoperations will include joint manipulations under anaesthesia or open reductions, debridements for infection, fixation for periprosthetic fracture and revisions for dislocation, infection or fracture (all in hip replacement arm); debridements for infection, revision fixation and revision to hip replacement (all in fixation arm). As dislocations are limited to those with a hip replacement, we will compare the rate of dislocation between those originally undergoing primary hip replacement and those receiving replacement after a failed fixation.

For consistency between the short and long-term economic analyses (the latter based on routinely collected data), we will compare the number of fracture-related inpatient stays and emergency department (ED) visits reported in the RCD datasets at 1 year, with the short-term, 12 months participant data on hospitalisations and ED attendances for each treatment group. This will help provide context for interpretation of the long-term follow-up.

11.6 Decision points

Clinical Research Protocol Template version 15.0 CONFIDENTIAL © Copyright: The University of Oxford and Oxford University Hospitals NHS Foundation Trust 2019 Page 23 of 27 A total of 878 participants will be randomised across a minimum of 40 recruitment centres. We will exploit the efficiencies available from nesting this within the Platform. This Platform has been built based upon the experiences of the TMG which has successfully delivered three hip fracture trials^{17 18 26} and three further trials are currently underway (ISRCTN92825709, 18393176, 15606075). The comparison processes are streamlined and harmonised with those of the Platform so that we should be able to achieve 65% recruitment of eligible patients and 90% follow-up of available participants (those alive and not withdrawn) at the primary outcome time-point.

During the 9 months internal pilot phase, we expect to recruit 80 patients from the 15 pilot recruitment centres. The DSMC and POC will closely monitor recruitment during the feasibility phase and make a recommendation to the funder regarding continued progress of the comparison against the specified stop/go criteria. If recruitment is below 60 participants, we will consider stopping the comparison for feasibility reasons; if between 60 and 80 participants we will review the recruitment processes and implement the committees' recommendations. In the event that recruitment is lower than anticipated we have a network of 120 hospitals in addition to these 40 that have previously worked with us on multicentre trials.

If the comparison is stopped, then all comparison participants will be followed up as per protocol. If the comparison continues into the main phase, participants from the internal pilot will be included in the final analysis.

Following the pilot phase, a minimum of a further 25 recruitment centres will be involved with recruitment, which will be completed within a total of 29 months. Those patients recruited during the pilot phase will be included in the final sample.

12 DISSEMINATION POLICY

The main outputs for FRUITI will be released within 12 months of the end of the main follow-up data collection time-point at 1-year post-diagnosis of a hip fracture. Outputs for the long-term analysis will be released within 12 months of the end of the final data collection time-point at 5 years post-diagnosis.

Trial slide-decks will be provided to clinicians through the network of WHiTE investigators and presented at local and regional multidisciplinary meetings. In addition, we will produce:

- Plain English outputs, led by the UK Musculoskeletal Trauma PPI group and distributed via paper, web and blog media
- Major international free-to-access publications including the protocol and Statistical Analysis Plan, as well as the main trial results
- National presentations Orthopaedic Trauma Society, Age Anaesthesia & British Geriatrics Society
- International presentations Global Fragility Fracture Network Congress, Orthopaedic Trauma Association Congress.

14 ANNEX A: FLOW CHART
